Patient name scored >=4 on MINI on CNICS PRO (date xx/xx/yyyy) and is eligible for the CBT4CBT (Computer Based Training for Cognitive Therapy) and APT intervention components. Based on study we recommend a prescription of tablet naltrexone 50 mg 1x/day with food. There were no chronic or current opioids listed and no LFTs >5xULN on medical record for this patient (checked on date: xx/xx/yyyy). We have also confirmed with participant about illicit opioid use since naltrexone may interact with opioids.

ARCH IRA study staff: Name

If Acomprosate Prescription

Subject: ARCH IRA study

Pt enrolled to ARCH IRA study: U01 AA020802 - Alcohol Research Consortium on HIV – Intervention Research Consortium

Enrolled on xx/xx/yyyy, with a AUDIT/AUDIT C score of XX

Patient name scored >=4 on MINI on CNICS PRO (date xx/xx/yyyy) and is eligible for the CBT4CBT (Computer Based Training for Cognitive Therapy) and APT intervention components. Based on study algorithm and consultation with [name]/ [name] we recommend a prescription of tablet acomprosate Two 333mg tablets 3x/day with or without food. The CrClearance was not <30 on medical record for this patient (checked on date: xx/xx/yyyy).

ARCH IRA study staff: Name

OR

Subject: ARCH IRA study

Pt enrolled to ARCH IRA study: U01 AA020802 - Alcohol Research Consortium on HIV – Intervention Research Consortium

Enrolled on xx/xx/yyyy, with a AUDIT/AUDIT C score of XX

Patient name scored >=4 on MINI on CNICS PRO (date xx/xx/yyyy) and is eligible for the CBT4CBT (Computer Based Training for Cognitive Therapy) and APT intervention components. Based on study algorithm we recommend a prescription of tablet acomprosate Two 333mg tablets 3x/day with or without food. The CrClearance was not <30 on medical record for this patient (checked on date: xx/xx/yyyy).

ARCH IRA study staff: Name

If Disulfiram Prescription

Subject: ARCH IRA study

Pt enrolled to ARCH IRA study: U01 AA020802 - Alcohol Research Consortium on HIV – Intervention Research Consortium

Enrolled on xx/xx/yyyy, with a AUDIT/AUDIT C score of XX

Patient name scored >=4 on MINI on CNICS PRO (date xx/xx/yyyy) and is eligible for the CBT4CBT (Computer Based Training for Cognitive Therapy) and APT intervention components. Based on study algorithm and consultation with [name]/ [name] we recommend a prescription of tablet disulfiram 250mg or 500mg 2 or 3x/day. There were no active prescriptions of ritonavir, tipinavir, metronidazole or any med containing alcohol on medical record for this patient (checked on date: xx/xx/yyyy).

ARCH IRA study staff: Name

OR

Subject: ARCH IRA study

Pt enrolled to ARCH IRA study: U01 AA020802 - Alcohol Research Consortium on HIV – Intervention Research Consortium

Enrolled on xx/xx/yyyy, with a AUDIT/AUDIT C score of XX

Patient name scored >=4 on MINI on CNICS PRO (date xx/xx/yyyy) and is eligible for the CBT4CBT (Computer Based Training for Cognitive Therapy) and APT intervention components. Based on study algorithm we recommend a prescription of tablet disulfiram 250mg or 500mg 2 or 3x/day. There were no active prescriptions of ritonavir, tipinavir, metronidazole or any med containing alcohol on medical record for this patient (checked on date: xx/xx/yyyy).

ARCH IRA study staff: Name

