[figure not shown]
Integration of Evidence-based Alcohol Intervention into HIV
Care (ARCH-IRA)

Study Protocol

NCT02938377

May 23, 2019

[name], Psy.D, Professor, Principal Investigator
University of Alabama at Birmingham
Birmingham, AL 35294

Integration of Evidence-based Alcohol Intervention into HIV Care (ARCH-IRA)

Study Protocol

Version 5
May 2019

Send Questions or Comments to:

[name] [contact]
[name] [contact]
[name] [contact]

STUDY OBJECTIVES

Aim 1: Examine effects of algorithm-guided alcohol treatment on alcohol consumption and alcohol use disorder (AUD) symptoms.

Hypothesis 1A: Patients who are treated using algorithm-guided alcohol treatment will decrease drinking quantity and or frequency compared to pre-algorithm levels.

Hypothesis 1B. Patients who are treated using algorithm-guided treatment will decrease current AUD symptoms compared to pre-algorithm symptoms levels.

Aim 2: Examine effects of algorithm-guided alcohol treatment on retention in HIV care and HIV-related outcomes.

Hypothesis 2A. Patients treated using algorithm-guided treatment will increase adherence to clinic visits and HIV medications compared to pre-algorithm levels.

Hypothesis 2B. Patients who receive algorithm-guided treatment will have improved HIV biomarkers (e.g., CD4 and viral load (VL)). Hypothesis 2C. There will be a positive relationship between VL and alcohol consumption measured by self-report and PeTH level.

Aim 3: Examine effects of algorithm-guided alcohol treatment on comorbid conditions (e.g., depression, anxiety, hepatitis C virus coinfection (HCV), and other drug use disorders).

Hypothesis 3A: Persons living with HIV (PLWH) with co-morbid depression and anxiety receiving algorithm-guided treatment will have better alcohol, mental health and HIV treatment outcomes compared to similar individuals in Standard of Care (SC).

Hypothesis 3B: PLWH with comorbid HCV receiving algorithm-guided treatment will have improved FIB4 results and reduced likelihood of HCV recurrence compared to persons in SC. Hypothesis 3C: Other drug use will decrease among those receiving algorithm-guided treatment vs SC.

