Aim 4: Characterize provider-, staff-, patient-, and clinic-level facilitators and barriers to integration of algorithm-guided alcohol treatment. We will examine the impact of factors such as provider knowledge and confidence, geographic setting, and clinic characteristics such as size, staffing patterns (e.g., number and type of staff, providers, etc.), average number of annual visits by patients, amount of Ryan White funding, and average appointment time.

STUDY ACTIVITIES

I. Study Population

About 756 participants will be recruited from 4 participating study sites (UAB, UW, UCSD, and JHU) over a 2-year enrollment period. The approximate number of participants enrolled at UAB would be 259, UW would be 115, UCSD would be 232, and JHU would be 150. Sites may over enroll if needed.

Inclusion criteria:

1. Age 18 years or older
2. Engaged in HIV care at one of the CNICS sites and enrolled in CNICS
3. The most recent AUDIT-C score ≥ 3 or 4 for women / ≥ 4 or 5 for men and MINI ≥ 1 , or AUDIT score ≥ 5 for women and ≥ 6 for men. For patients who identify as transgender, the female scoring cut off for AUDIT-C/AUDIT will be used.
4. English speaking
5. Able and willing to provide informed consent

Exclusion criteria:

1. Non-English speaking;
2. Suicidal ideation as measured by answering item #9 of PHQ 9 “almost every day” which triggers the CNICS suicidal ideation pager alert. This is from most recent PRO (same as AUDIT-C and AUDIT scores). Having answered PHQ9 with “almost every day” on prior PHQ-9 item #9 in the distant past does not meet exclusion criteria.
3. Unable to provide informed consent.
4. Provider refusal

II. Screening

Patients who are eligible to take the CNICS PRO on the same day as their Primary Care Provider (PCP) visit will be screened for the ARCH IRA study based on the inclusion criteria mentioned above. The CNICS PRO will indicate if the patient is eligible/ineligible for the study.

A. AUDIT and AUDIT-C Eligibility Information

The ARCH-IRA study will use the most recent AUDIT-C or AUDIT score to determine continued eligibility. A lower cutoff was selected to be more inclusive and maximize recruitment of potentially eligible participants. This choice is justified as people often under-report bad or socially undesirable behaviors such as risky sex, drug, and alcohol use.

	Women / Transgender	Men
AUDIT-C	≥ 3 or 4 and MINI ≥ 1	≥ 4 or 5 and MINI ≥ 1
AUDIT	≥ 5	≥ 6

Example of continued eligibility:

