Jane scored a 4 on the AUDIT-C and a 2 on the MINI on her PRO. After a page was received (please see page XXX for more information on pages), ARCH-IRA study staff approaches Jane in clinic. Jane decided to postpone enrollment until her next clinic visit in 6 months. Jane will need to complete a new PRO at her clinic visit in 6 months.

- If she does not complete a PRO during her clinic visit, the ARCH-IRA study staff can still approach for enrollment into ARCH-IRA.
- If she does complete a PRO during her clinic visit and she her new AUDIT-C score is a 2, then Jane is no longer considered eligible for ARCH-IRA and study staff will not approach.
- If she does complete a PRO during her clinic visit and she her new AUDIT-C score is a 6 and study staff received a new Peedy page, then Jane can be approached again for enrollment.

III. Randomization

Randomization will be programmed into the CNICS PRO platform. Controls will not be approached for any study activity. Study staff will receive pages for only intervention participants. Randomization process occurs before the consenting takes place. It is a 5:1 assignment for intervention and controls. Intervention vs. control status will be tracked in the PRO platform.

IV. Peedy alerts

If a patient meets the eligibility criteria (page XXX) for ARCH-IRA, a Peedy alert is generated through the CNICS PRO platform, which is developed and run by the UW team. A Peedy alert can come through as a page and/or an email to the appropriate study staff. Each page and/or email sent will include the following: patient's ticket number (ticket generated through CNICS, valid only 48 hours); the PRO session number; and the version of Peedy the patient is eligible for (please refer to page XXX for more information on the different versions of Peedy).

A. UAB

Study staff will approach eligible patients in clinic after receiving the Peedy alert. Staff will follow the ARCH-IRA recruitment script (Appendix 3) when approaching in clinic.

B. UW

The UW will use the same script and approach as UAB and will document status including refusals and reasons in the tracking log/PRO platform. (**Note at UW: there is likely not a handoff between two staff members as described above for UAB but instead the same staff member will proceed with the consent process if the participant is willing.)

C. UCSD

TBD

D. JHU

TBD

V. Enrollment and Informed Consent

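### Hypotheses 1A, 1B and 2A measure success against treated patients' own earlier level, not the randomised controls, so regression to the mean alone could satisfy 1A

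*Protocol*

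**What the plan says.** All references are to the protocol.

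- **Study Objectives, Aim 1.** 1A: "Patients who are treated using algorithm-guided alcohol treatment will decrease drinking quantity and or frequency compared to pre-algorithm levels". 1B: "Patients who are treated using algorithm-guided treatment will decrease current AUD symptoms compared to pre-algorithm symptoms levels".
- **Study Objectives, Aim 2.** 2A predicts that treated patients "will increase adherence to clinic visits and HIV medications compared to pre-algorithm levels". 2B says "Patients who receive algorithm-guided treatment will have improved HIV biomarkers" and gives no comparator. 2C is an association and is not in question here.
- **Study Objectives, Aim 3.** Standard of Care (SC) appears as comparator only here. 3A does compare alcohol and HIV outcomes with SC, but only in patients with comorbid depression and anxiety.
- **I. Study Population, inclusion criterion 3.** "The most recent AUDIT-C score ≥ 3 or 4 for women / ≥ 4 or 5 for men and MINI ≥ 1", or a full AUDIT score at or above 5 (women) or 6 (men).
- **III. Randomization.** "It is a 5:1 assignment for intervention and controls", and "Randomization process occurs before the consenting takes place". Controls are not approached, but their status is tracked in the PRO platform.

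The term for the before value is not defined. Two passages point to the screening questionnaire: VI.E places visit 1 on the day of the CNICS PRO, and VI.A.ii counts reduced drinking from visit 1.

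**The concern.** A group chosen because a fluctuating score lies above a cut-off will, on average, score lower when measured again, treated or not. If the selecting score is also the before value, 1A predicts something that would happen anyway. The same holds for 1B in patients who enter through the AUDIT-C route, since MINI of at least 1 is part of that criterion. For patients who enter on AUDIT alone, the effect on MINI symptoms is indirect and smaller.

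2A and 2B concern adherence and HIV biomarkers, on which nobody is selected. Their weakness is different: a before-after change cannot be separated from time trends in clinic care.

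The randomised controls remove regression to the mean, time trends and the effect of repeated questioning together. They are already in the design, yet the hypotheses on drinking, symptoms, adherence and biomarkers in the whole study population do not name them.

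**Working it through.** **Figures in the protocol.** The site targets give 259 + 115 + 232 + 150 = 756, as stated. The protocol shows no power calculation to reproduce. If 756 covers both arms, 5:1 gives 756 × 5/6 = 630 treated and 756/6 = 126 controls. If 756 is intervention only, there are about 756/5 = 151 controls.

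**Assumptions, not in the protocol.** Normally distributed scores; screening PRO as baseline; test-retest correlation r of 0.6 to 0.9; top 15% to 40% of screened patients selected; no treatment effect.

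**Formulas.** With c the cut-off in SD units and λ = φ(c)/P(Z>c):

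- expected fall = (1 − r)λ
- variance of change = (1 − r)²(1 + cλ − λ²) + (1 − r²)
- paired z = √n × fall / SD of change
- n for 95% power at two-sided 5% = (3.605 × SD of change / fall)²

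| Selected, r | Fall (SD) | SD of change | z, n=630 | z, n=756 | z, n=315 | n for 95% power |
|---|---|---|---|---|---|---|
| top 15%, 0.6 | 0.622 | 0.819 | 19.05 | 20.87 | 13.47 | 23 |
| top 25%, 0.7 | 0.381 | 0.729 | 13.13 | 14.38 | 9.28 | 48 |
| top 40%, 0.9 | 0.097 | 0.439 | 5.52 | 6.04 | 3.90 | 269 |

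The column for 315 represents losing half of 630. Simulating two million pairs gave falls of 0.619, 0.382 and 0.096.

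**A more inclusive cut-off.** At r = 0.9 and n = 630, z is about 3.7 if the top 60% are selected and about 2.0 if the top 80% are.

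**Outcomes not used for selection** (MINI in AUDIT-only entrants, PeTH). Fall = ρ(1 − r)λ, with an assumed correlation ρ with the screening score of 0.3 to 0.7. This gives 0.3 × 0.097 = 0.029 SD up to 0.7 × 0.622 = 0.435 SD.

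**Within-arm against between-arm test.** In 4,000 simulated trials of 630 versus 126 with no treatment effect, the within-arm test showed a significant fall in 100% of runs and the between-arm test was significant in 5.2%. This held both for the top 30% with r = 0.7 and for the top 40% with r = 0.9.

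**What the between-arm comparison can detect.** At 80% power, two-sided 5%, unadjusted: 2.80 × √(1/n₁ + 1/n₀).

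- 630:126 gives 0.273 SD; 756:151 gives 0.250 SD.
- With an assumed 20% loss, dividing by √0.8: 0.306 and 0.279 SD.
- With an assumed uptake of 80% or 60% at 630:126 without loss, the effect needed among treated patients is 0.273/0.8 = 0.342 or 0.273/0.6 = 0.456 SD.
- If 756 counts only consented intervention patients, those randomised number 756/0.8 = 945 with 189 controls, or 756/0.6 = 1260 with 252 controls. The effect needed among treated patients is then 0.223/0.8 = 0.279 or 0.193/0.6 = 0.322 SD.

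**The case against.** The protocol states directional hypotheses, not tests or decision rules. Testing is usually left to the SAP, which is not at hand and may well compare the arms. That is fair, and no absent SAP content is faulted. But the comparator is stated here. An SAP that follows 1A as worded inherits the bias, and one that compares the arms answers a different question from 1A.

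The baseline is undefined, and the supporting passages concern a video assignment rule and blood-spot timing. The worked example in section II also lets a patient enrol about six months later without a new PRO, so the enrolment visit and the selecting score need not coincide. This stands as a limit on size. With an earlier PRO as baseline the fall would be smaller, and zero if both intervals have the same correlation. The comparator would still not be the randomised one, and time trends and repeated questioning would remain.

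Section II.A calls the cut-off a lower, inclusive one, the real entry rule combines instruments, and AUDIT-C is short and bounded. So the z values illustrate a simple model and do not forecast this trial. The direction does not depend on these details, and the extended check above shows how inclusive the cut-off must be before the problem becomes marginal.

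Section III says controls, not SC. Treating them as the same group is an inference, though no other comparison group is described.

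Finally, moving from treated patients to all randomised patients changes the target of inference and lowers precision. This is true and is the real cost of the change.

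**Conclusion.** The concern holds. As worded, 1A can be met by an ineffective algorithm, and so can 1B for patients selected on the MINI. With the screening PRO as baseline and the assumed ranges, the untreated fall is 0.10 to 0.62 SD, and 23 to 269 patients would be enough for 95% power to call it significant, well below the 630 or 756 planned. The size depends on the assumed selection fraction, correlation and normality, and on how the baseline is read; the direction, given that baseline, does not. For 2A and 2B the claim is limited to the missing control for time trends. This should be corrected before analysis, because it affects the first hypothesis of the first aim and the remedy is already in the design.

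**What to change.** Restate 1A, 1B, 2A and 2B as intervention versus SC by randomised assignment, and say that SC means the randomised controls. Include everyone randomised, also intervention patients who refuse or are never approached. Because randomisation precedes consent, comparing only consenting intervention patients with all controls would lose the protection of randomisation. Take outcomes from CNICS PRO and clinic data in the same time window in both arms, adjusted for site and for the value at the randomising PRO, and define the pre-algorithm level as that PRO. Keep within-arm change as description only. The same applies to PeTH change, because controls give no study blood spots.

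The cost is the rewording of four hypotheses and one baseline definition. It assumes that routine CNICS data on controls and refusers may be used for this purpose and arrive in comparable windows; entry requires CNICS enrolment, which makes this plausible. The statistical price is the lower precision and the dilution by non-uptake calculated above. PeTH cannot become a between-arm outcome without new sampling.

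### Hypotheses 3A to 3C compare patients receiving the algorithm with standard of care, although consent follows randomisation and is sought in one arm only; the contrast should be by assigned arm

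*Protocol*

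**What the plan says.** Aim 3 (Study Objectives) contains the only hypotheses that name the SC comparator. In each, the intervention side is described by receipt:

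- 3A: people with "co-morbid depression and anxiety receiving algorithm-guided treatment will have better alcohol, mental health and HIV treatment outcomes", set against similar individuals in SC.
- 3B: "PLWH with comorbid HCV receiving algorithm-guided treatment will have improved FIB4 results", with a lower likelihood of HCV recurrence, set against persons in SC.
- 3C: "Other drug use will decrease among those receiving algorithm-guided treatment vs SC".

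Section III (Randomization) fixes the sequence: "Randomization process occurs before the consenting takes place". Allocation is 5:1, staff are paged for intervention patients only, controls are not approached for any study activity, and assigned status is tracked in the PRO platform. Section V requires consent before any study activity. Section I lists "Able and willing to provide informed consent" as an inclusion criterion and "Provider refusal" as an exclusion. Section VII provides statuses for patients who are not approached, who postpone or who refuse. It also provides statuses for consented patients who decline the video, CBT4CBT or pharmacotherapy.

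**The concern.** One side of the contrast is defined by a choice made after randomisation, the other by assignment. Patients assigned to the intervention who decline drop out of the first group. Their counterparts among the controls stay in the second, because nobody asks them. The similarity required in 3A cannot repair this, since willingness to consent is never observed in controls.

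Consenters and refusers may have different outcomes whatever the algorithm does. The decline reasons in Appendix 3 point both ways: a patient who does not want to change may do worse, while one who denies an alcohol problem may be a milder drinker. A contrast by receipt mixes this difference with the effect of the algorithm. A contrast by assignment does not.

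Two further steps may add to the filter, but the text does not settle it. The timing of provider refusal is not stated. The re-check after postponement (Section II.A: "The ARCH-IRA study will use the most recent AUDIT-C or AUDIT score to determine continued eligibility") is not limited to one arm.

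**Working it through.** **Stated figure.** The site targets add up: 259 + 115 + 232 + 150 = 756. No power calculation is given, so there is none to reproduce. The protocol does not say whether 756 includes controls.

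**Bias.** Let c be the share who consent, or would consent if asked, and d the consenter–refuser difference in the outcome as analysed. Under no treatment effect:

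- intervention receivers have the consenter mean, m;
- controls have c·m + (1 − c)(m − d) = m − (1 − c)d;
- spurious difference = (1 − c)d.

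It is zero if d = 0. If change from baseline is analysed, a stable level gap cancels, and d is then the gap in change.

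**Inputs.** From the protocol: 756 and 5:1. Reading 756 as both arms gives 630 and 126. Assumed: c, d, SD = 1, a two-sided 5% test, and a 30% comorbidity subgroup for 3A and 3B.

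**Formula.** Rejection = P(|Z + (1 − c)d/SE| > 1.96), with SE = √(1/n₁ + 1/n₂), n₁ = 630c and n₂ = 126. In the subgroup both are multiplied by 0.3.

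| Sample | c | d (SD) | n₁ vs n₂ | Bias (SD) | SE | Rejection under the null |
|---|---|---|---|---|---|---|
| Whole (3C) | 0.8 | 0.1 | 504 vs 126 | 0.02 | 0.0996 | 5.5% |
| Whole (3C) | 0.5 | 0.3 | 315 vs 126 | 0.15 | 0.1054 | 29.6% |
| 30% subgroup (3A, 3B) | 0.8 | 0.1 | 151.2 vs 37.8 | 0.02 | 0.1818 | 5.1% |
| 30% subgroup (3A, 3B) | 0.5 | 0.3 | 94.5 vs 37.8 | 0.15 | 0.1925 | 12.2% |

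With d = 0 the rejection rate is 5.0% at any c.

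**Other reading of 756.** If 756 counts consented intervention patients only, c = 0.5 implies 756/0.5 = 1,512 assigned and 1,512/5 ≈ 302 controls. Then SE = √(1/756 + 1/302.4) = 0.068, 0.15/0.068 = 2.2, and whole-sample rejection is about 60%. The table therefore shows the lower figures.

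**Dilution under the fix.** Assume a 0.3 SD effect in receivers and that every consenter receives the algorithm. By assignment (630 vs 126, SE 0.0976):

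- c = 0.5: effect 0.3 × 0.5 = 0.15 SD, power 34%;
- c = 0.8: effect 0.3 × 0.8 = 0.24 SD, power 69%.

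By receipt, if there were no selection at all: 315 vs 126 gives 81%, and 504 vs 126 gives 85%.

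**The case against.** The strongest reply is that *receiving* is shorthand for the arm. SC is an arm name. Section III speaks of intervention participants before anyone has consented, assignment is tracked, and the outcome of every alert is recorded. The protocol nowhere says that refusers will be excluded, and which randomised patients enter an analysis is often left to the SAP. This reading is possible. But no passage adopts it, and in this design assignment and receipt are recorded as different things. The point does not complain of missing detail: it concerns the contrast that the protocol itself states. An SAP that followed that wording would carry the bias, and one that analysed by assignment would depart from it.

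The reply is right that the magnitude rests wholly on assumed inputs and that its low end is indistinguishable from 5%. It is also right that 3C speaks of a decrease and 3B of improvement, which suggests change. A stable level gap would then cancel, and the 30% figure for 3C would need a 0.3 SD gap in change in other drug use. The protocol gives no evidence of one. Nor are provider refusal and re-screening shown to act in one arm only. These points limit what can be said about size. They do not make the stated contrast a randomised one.

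**Conclusion.** The concern holds and should be fixed; confidence is medium because the arm-label reading cannot be excluded. As worded, 3A to 3C select one randomised arm on a post-randomisation choice and leave the other intact. The bias is (1 − c)d, of unknown size and sign. Over the assumed range, from 80% consent with a 0.1 SD gap to 50% with 0.3 SD, it runs from 0.02 to 0.15 SD. A nominal 5% test then rejects in 5.5% to about 30% of null trials in the whole sample, and in 5.1% to about 12% in a 30% subgroup. These figures take 756 as both arms and d as the gap in the outcome as analysed.

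**What to change.** Restate 3A to 3C as comparisons by randomised assignment among all PRO-eligible patients randomised in the platform. For 3A and 3B, define the comorbidity subgroup at baseline and identically in both arms. Take outcomes from routine CNICS data for both arms. Add one sentence: consent, provider refusal and re-screening after postponement govern delivery of the intervention, not membership of the analysis set. Inclusion criterion 5 and exclusion criterion 4 need to be read in the same way. Any by-receipt estimate should be secondary and respect randomisation, for example a complier-average effect. If *receiving* already meant assigned, saying so is enough.

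The text change is small, and assignment and refusals are already recorded. There are two real costs. The effect is diluted by non-uptake; the higher power of the by-receipt contrast is available only if there is no selection, which cannot be checked here. The sponsor must also confirm that CNICS consent covers the routine data of patients who refuse this study. That controls' outcomes come from CNICS is itself inferred from their never being approached, and should be stated.

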Enter user name: uabmcD0

Password: BU6007

Click Reports, select start and end date and click 'generate'.

D. Alcohol Pharmacotherapy (APT)

During visit 1, participants who have scored AUD on MINI would become eligible to receive Alcohol Pharmacotherapy (APT).

Providers/PCC/study staff can call/page [name]/ [name] in case they have questions on medications.

Information for [name]:

- ✓ [contact]
- ✓ [contact]
- ✓ Email: [contact]

Information for [name]:

- ✓ [contact]
- ✓ [contact]
- ✓ Email: [contact]

In instances where you cannot reach them by phone and need to leave a VM.

VM to leave: *Hi this is 'XYZ', I have a question on ARCH IRA participant who is in the clinic/ or not in the clinic (use as appropriate). Please call back at 'phone number'.*

Paging instructions:

- Go to <https://www.paging.uab.edu/>
- Enter the last 4 digits of the pager number or name in the box and click search. You will see name and pager number that pops up.
- Click the pager number which is bold and green and a screen will come up saying enter your message and send button. You can only enter 80 characters for message.
- Enter message and click hit send.
- Message to send: *Question on ARCH IRA participant. Call back on 'phone number'.*

i. UAB

Study staff/PCC will use the APT algorithm ([Appendix 1 Algorithm 2](#)) and the EMR to determine which medication to recommend to the provider. Study staff/PCC will communicate with participant's provider in clinic and/or send a message through the EMR and recommend a drug from the APT list. These recommendations will be done based on APT algorithm plus consultation with PI ([name]) of the study/addiction specialist ([name] [name]) on case-

by-case basis via email or phone communication. Template scripts of these recommendations can be found in **Appendix XX**.

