If APT is prescribed to the participant, study staff/PCC will communicate with participant about the side effects of the recommended drug (described in Appendix 2 under medication list) and make sure that the participant understands to call study staff/PCC and clinical care team in case s/he experiences any side effects. In addition, study staff/PCC will follow up with participants in one week to see how they are doing on their medication. Attempts will be made up to one month following receipt of medication. Study staff/PCC will call twice per week in attempting to reach the participant. If participant reports a side effect, the study staff/PCC will inform the participant's clinical care team using message center in the Cerner. The provider will determine the course of action to be taken (e.g., continue, reduce dose, and discontinue medication). [name]/ [name] will be available for provider to consult about medication.

ii. UW

A similar set of procedures will be used for most of these steps at the UW.

Providers will receive a notification for patients eligible for APT:

XX is participating in the ARCH-IRA study and reported at-risk alcohol use on the clinical assessment. Based on XX's risk, he is eligible and would likely benefit from Alcohol Pharmacotherapy (APT). Naltrexone is most often recommended for APT unless the patient has acute hepatitis or liver failure (LFTs>5x ULN) or is currently using prescribed or illicit opioids. The dose of naltrexone is 50 mg PO per day. We have attached an APT medication algorithm and list of medications and doses for your information. We hope this information is useful to you and that you consider whether prescribing APT would be of benefit to George.

At UW, this message can be sent through Epic with algorithm attached or printed and handed directly to provider. The assessment of appropriateness of specific APT choices based on LFTs or opiate use will be assessed by and at the discretion of the patient provider. The PCC will contact participants as above and address issues with participant regarding access, receipt of, and other issues with APT but side effects will be deferred to clinical staff.

iii. UCSD

TBD

iv. JHU

TBD

E. Dried Blood Spots

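### Does Aim 4 promise effects of geography and clinic characteristics that four sites cannot deliver?

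*Protocol*

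**What the plan says.** Under Study Objectives, the heading sentence of Aim 4 is "Characterize provider-, staff-, patient-, and clinic-level facilitators and barriers to integration of algorithm-guided alcohol treatment". The next sentence reads "We will examine the impact of factors such as provider knowledge and confidence, geographic setting, and clinic characteristics such as size, staffing patterns", and after an aside on staffing it ends with "average number of annual visits by patients, amount of Ryan White funding, and average appointment time". Aims 1 to 3 each carry lettered hypotheses; Aim 4 has none. The protocol names no outcome, model, test, significance level or sample-size argument for Aim 4.

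Section I (Study Population) states: "About 756 participants will be recruited from 4 participating study sites (UAB, UW, UCSD, and JHU) over a 2-year enrollment period". It gives the approximate numbers as "enrolled at UAB would be 259, UW would be 115, UCSD would be 232, and JHU would be 150", and allows sites to exceed them. It does not say how many clinics make up a site, or whether the clinic characteristics are recorded once or repeatedly.

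Section VI.D (Alcohol Pharmacotherapy) describes delivery site by site. At UAB, staff contact the provider in clinic or "send a message through the EMR and recommend a drug from the APT list". At UW, the suitability of "specific APT choices based on LFTs or opiate use will be assessed by and at the discretion of the patient provider". The entries for UCSD and JHU are still to be written.

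**The concern.** To examine the impact of a factor is the language of effects. Geography belongs to a site, and clinic size, staffing, visit frequency, funding and appointment length may well be fixed for a site too. If so, the number of independent observations on them is the number of sites, four, and not the number of patients, 756. Patients are randomized individually through the PRO platform, so clinic characteristics are not randomized and differ along with everything else that distinguishes one site from another, including how pharmacotherapy advice reaches the provider.

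At stake is a conclusion such as that better funding or longer appointments help integration. It would rest on four points and could reflect any other difference between those sites. Because the protocol sets both the aim and the number of sites, it can seem that no later document could repair this. Aims 1 to 3, and the provider-, staff- and patient-level parts of Aim 4, are not touched.

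**Working it through.** **Inputs from the protocol.** Four sites with targets 259, 115, 232 and 150 (section I). Factors named in Aim 4 that could be constant within a site: geographic setting, clinic size, staffing patterns, annual visits, Ryan White funding and appointment time, so at least six.

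**The plan's own figure.** 259 + 115 + 232 + 150 = 756, which matches the stated total.

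**Assumption.** Each of the six factors takes a single value per site. The protocol neither states nor excludes this.

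**Separability.** An intercept plus six site-constant factors needs 1 + 6 = 7 parameters. Four sites give a design matrix of rank 4, whatever the number of patient rows. So at most 4 − 1 = 3 site-level contrasts can be estimated, and none is then left for residual variation. Over-enrolment adds rows but no rank.

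**If someone chose to test one factor across the site means.** Residual degrees of freedom are 4 − 2 = 2, and the two-sided 5% critical value is t = 4.303. The correlation needed is

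|r| = t / √(df + t²) = 4.303 / √(2 + 4.303²) = 0.950.

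An exact two-sided rank-correlation test on four sites cannot give a p-value below 2/4! = 2/24 = 0.083. With two factors together, 1 degree of freedom is left and the critical t is 12.7.

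**What these results bear on.** The rank count follows from the protocol's numbers and the constancy assumption. The critical correlation and the minimum p-value describe a test at a 5% level that the protocol does not propose. Power figures or a design effect would need a true correlation or an intraclass correlation as well, and the protocol gives neither. Such figures would measure the weakness of an analysis that nobody has planned, so they do not size a fault in this document.

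**The Aim 4 wording set side by side.**
- Heading sentence: characterize facilitators and barriers. This is descriptive.
- Second sentence: examine impact. This is looser and could be read as causal.
- The factors are introduced as examples, so there is no commitment to estimate each one or all of them jointly.
- Aim 4 has no hypothesis, unlike Aims 1 to 3.

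On balance the text permits a descriptive treatment and requires no inferential one.

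**The case for a change.** The strongest case for a change is that separability does not depend on testing. Even without a p-value, an estimate of one characteristic's impact from four sites is tangled up with the other characteristics. An analysis plan can choose a model but cannot add sites. The heading verb allows description, but the following sentence does not limit the aim to it. Confounding is also visible in the text, since pharmacotherapy advice is handled differently at UAB and UW. Rewording one sentence would cost almost nothing.

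The identifiability limit stands, given constancy within site. The rest is weaker.

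- The harm feared is an unsupported conclusion, and an analysis plan can prevent that. It can state that site-level factors are described, and keep inference to provider, staff and patient factors with site as a fixed effect. Neither step conflicts with Aim 4 as written.
- The constancy assumption may fail. Several clinics per site, or changes in staffing and appointment length over the two-year enrolment period, would ease the limit for clinic characteristics, though less so for geography.
- The contrast between UAB and UW is narrower than it first appears. UW says it follows much the same steps for most of the process, and its notice to providers names the drug usually suggested and attaches the algorithm and medication list. At UAB, too, staff only recommend. The unwritten UCSD and JHU entries are unfinished text and document no difference.
- The low cost of rewording does not create a gain: no data item, sample size or planned result would change.

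**Conclusion.** No change to the plan is needed. To the extent that geography and clinic characteristics are constant within a site, four sites support at most three between-site contrasts for at least six named factors. Results on these factors should therefore be read and reported as a descriptive four-site comparison. This is a note on how to interpret one loosely worded sentence. The protocol promises no test or separate effect estimate for these factors, and no stated rule, figure or analysis would give a wrong answer if followed. The statistical analysis plan, which was not at hand, is the natural place to settle the point and may already do so. The conclusion rests on reading Aim 4 by its heading verb and its lack of a hypothesis. It would change if the study proposed a formal test, or claimed a separate effect of a named clinic characteristic, on the strength of the four sites alone.
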